##### **6.4.2 Key Secondary Analysis**

#### 6.4.2.1 Change from Baseline in log10 Viral Load

Log10 viral load, as assessed using the saliva and as assessed using the nasal swab, will be summarized by treatment group using descriptive statistics (N, mean, median, standard deviation, minimum, and maximum) for each visit as well as for changes from baseline where an 80% CI will also be presented.

Mean changes from baseline will be analyzed using a repeated measures ANCOVA model including effects of treatment, visit (Day 3, Day 5, Day 10 and Day 28/EOS), and treatment-by-visit interaction, as well as baseline value of log10 viral load and baseline value of log10 viral load-by-visit-interaction. An unstructured covariance structure will be used to model the within-patient errors and the Kenward-Roger approximation will be used to estimate denominator degrees of freedom. The combined two highest treatment groups will be compared to placebo in addition to the comparison of individual doses at the following study visits (Day 3, Day 5, Day 10 and Day 28/EOS).

Since oragene and nasal samples are collected by the subjects themselves (visit identifiers may be unreliable), an algorithm (presented in Appendix 2) was developed to classify the day of assessment into their respective visit identifiers. This algorithm is based on the fact that Day 1 corresponds to the date of the first dose and as such, will be used as baseline when available. This is in alignment with the study protocol that identifies Day 1 as the date of first dose. It is understood that all protocol assessments collected on Day 1 were to be done PRIOR to the first dose. Therefore, Day 1 will correspond to baseline when available. Please refer to Appendix 2 for more details.

A plot of mean change from baseline in log10 viral load with 80% CI at each study visit will also be presented (Section 7, Figure 4).

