### 4.1. Inclusion Criteria

Patients must satisfy all of the following criteria unless otherwise stated:

1. Willing and able to provide informed consent
2. Male or female patients > 18 years of age on the day of informed consent
3. Have received a confirmed diagnosis of COVID-19 (positive for SARS-CoV-2), as assessed by PCR or point-of-care within 72 hours of first dose on Day 1
4. Have mild to moderate signs or symptoms of COVID-19 with onset within 5 days of first dose on Day 1, at least two of the following symptoms:
  - stuffy or runny nose
  - sore throat
  - shortness of breath
  - cough
  - fatigue
  - myalgia
  - headache
  - chills or shivering
  - feeling hot or feverish
  - nausea
  - vomiting
  - diarrhea
  - anosmia
  - ageusia
5. Outpatient with COVID-19 disease (not requiring oxygen therapy [WHO COVID-19 Clinical Improvement Ordinal Scale, score of 3])
6. Patient is aware of the investigational nature of this study and willing to comply with protocol treatments, blood tests, and other evaluations listed in the ICF.

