### 6.3.4 Demographic and Baseline Characteristics

Demographic data such as age, sex, ethnicity, race and smoker will be summarized overall and by treatment group for the ITT population.

In case the date of birth is incomplete [in the eCRF Demographics], the following imputation will be done:

- the partial date will be replaced by the fifteenth day of the month if month and year are known;
- the partial date will be replaced by the first day of July if only the year is known.

A listing of demographic data will be provided (Section 7, Listing 4).

Medical and surgical history such as diabetes, hypertension, prior cardiovascular disease, respiratory disease, renal disease and liver disease will also be summarized overall and by treatment group for the ITT population.

Delays since first symptoms of COVID-19 will be summarized overall and by treatment group, for the ITT population. The number of days between the date of first symptom of COVID-19 and the following dates will be presented in this table: date of positive diagnosis for COVID-19, date of randomization and date of first dose of study medication. In addition, the number of days between the date of positive diagnosis of COVID-19 and the date of randomization will be presented, as well as how the diagnosis of COVID-19 was established.

Delays will be calculated as:

- Date of positive diagnosis for COVID-19 - Date of first COVID-19 symptoms
- Date of randomization - Date of first COVID-19 symptoms
- First treatment start date - Date of first COVID-19 symptoms
- Date of randomization - Date of positive diagnosis for COVID-19

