##### **6.4.1 Primary Analysis**

The primary endpoint is time to sustained clinical resolution of symptoms (excluding cough, sense of smell and taste) as determined by symptom score. Sustained clinical resolution of symptoms (excluding cough, sense of smell and taste) is defined in Section 4.1. Time to sustained clinical resolution will be calculated as date of resolution – date of randomization + 1. Subjects who did not resolve will be censored at the last time point where they were not resolved [see Section 9 Appendix 1]. The number and percentage of patients whose symptoms resolved will be presented, and to summarize the time to resolution, censored subjects will be imputed with a time to resolution of 29 days and simple medians with 80% confidence intervals will be provided.

The differences in time to sustained clinical resolution of symptoms (excluding cough, sense of smell and taste) between the treatment groups will be evaluated using 2-sided log-rank tests. The combined two highest treatment groups will be compared to placebo in addition to the comparison of individual doses.

The cumulative incidence curve for sustained clinical resolution (excluding cough, sense of smell and taste) will also be presented using 1 – Kaplan-Meier estimates(Section 7, Figure 2). Should there be several deaths, the cumulative incidence curve will be presented under a competing risk model.

A listing with the score of each symptom at each time point will be provided (Section 7, Listing 7).

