#### 6.4.2.2 AUC in log10 Viral Load

The area under the curve (AUC) of log10 viral load, as assessed using the saliva and as assessed using the nasal swab, will be calculated from randomization to Day 10 and summarized by treatment group using descriptive statistics (N, mean, median, standard deviation, Q1, Q3, minimum, and maximum). The AUC will be calculated using the trapezoidal rule on the period from baseline to Day 10. In subjects who will not have a viral load assessment up to Day 10, the last observation carried forward will be used so that the AUC is calculated on 10 days in all subjects. An ANOVA model will be performed to analyze the difference between treatment groups. The model will include only the treatment group. Contrasts under this model will allow for the comparisons across treatment groups. The results will be presented as mean treatment difference with associated 80% CI and p-value.

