#### **6.4.3.4 Change from Baseline in COVID-19 Total Symptom Score**

COVID-19 total symptom score will be summarized by treatment group using descriptive statistics (N, mean, median, standard deviation, minimum, and maximum) for each visit as well as for changes from baseline where an 80% CI will also be presented.

Mean changes from baseline will be analyzed using a repeated measures ANCOVA model including effects of treatment, visit (Day5, Day10, Day14 & Day28/EOS), and treatment-by-visit interaction, as well as baseline value of total symptom score and baseline value of total symptom score-by-visit-interaction. An unstructured covariance structure will be used to model the within-patient errors and the Kenward-Roger approximation will be used to estimate denominator degrees of freedom. The combined two highest treatment groups will be compared to placebo in addition to the comparison of individual doses at the following study visits (Day5, Day10, Day14 and Day 28/EOS).

Symptom scores were either reported electronically by the subject or by the site through telephone calls. Except for the assessments done at screening reported in the eCRF, no visit identifiers were attached to these evaluations, only the date of the assessment. Therefore, similar to viral load, the day of assessment of the symptom scores will be classified into visit identifiers as per the algorithm presented in Appendix 2. This will ensure that Day X for symptom score will correspond to Day X for viral load.

A plot of mean change from baseline in COVID-19 total symptom score with 80% CI at each study visit on the ITT population will be presented (Section 7, Figure 6).

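### Days from first symptom to first dose is collected but enters no efficacy analysis; the clearest gap is the treatment-only AUC model for viral load

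*SAP*

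**What the plan says.** Protocol 4.1, inclusion criterion 4, admits patients with symptoms "with onset within 5 days of first dose on Day 1". SAP 6.3.4 derives "First treatment start date - Date of first COVID-19 symptoms" and uses it descriptively: "Delays since first symptoms of COVID-19 will be summarized overall and by treatment group, for the ITT population".

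The SAP's efficacy analyses adjust as follows:

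- **Viral load, repeated measures (6.4.2.1):** treatment, visit and their interaction, "as well as baseline value of log10 viral load and baseline value of log10 viral load-by-visit-interaction".
- **Viral load AUC (6.4.2.2):** "The model will include only the treatment group".
- **Total symptom score, repeated measures (6.4.3.4):** treatment, visit and their interaction, "as well as baseline value of total symptom score and baseline value of total symptom score-by-visit-interaction".
- **Time to sustained resolution (6.4.1):** group differences "will be evaluated using 2-sided log-rank tests", with no strata named. The other time-to-event endpoints use the same methods.
- **WHO scale (6.4.3.5):** an unadjusted rank test.
- **Hospitalization, oxygen therapy, duration of hospitalization, mortality (6.4.3.6 to 6.4.3.9):** treatment only.

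Randomization is stratified by symptom severity and age (Protocol 5.3), and so are the protocol's own analyses (Protocol 8.3 and 8.4.1.1). Delay is a stratum in neither. SAP Section 1 places more emphasis on viral load and less on symptom endpoints when proof of concept is judged.

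**The concern.** Two patients with the same baseline viral load, one treated on the day of onset and one five days later, may be at different points of the illness. If so, part of the spread in their later viral load and recovery could be explained by a value known before treatment. Leaving it out puts that part into the residual.

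Two things are at stake. The first is precision, with 52 patients per arm and 104 against 52 in the main contrast. The second is chance imbalance. Because delay is not a randomization stratum, the arms can differ in mean illness day. The descriptive table would show that difference, but no planned analysis would allow for it, and an adjustment chosen after unblinding would be post hoc.

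The gap is plainest for AUC, a viral load analysis listed as key secondary. It omits even the baseline viral load that the SAP uses one subsection earlier.

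**Working it through.** **The plan's own figures.** The documents give no figure for the prognostic strength of delay. Their power figure is 127 resolution events for 80% power at HR 1.4 and alpha 0.2 (Protocol 8.1). Schoenfeld's formula with one third of patients on placebo is

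events = (z_alpha + z_power)² / [(1/3)(2/3)(ln 1.4)²].

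- One-sided 0.2: (0.842 + 0.842)² / 0.02516 = 113.
- Two-sided 0.2: (1.282 + 0.842)² / 0.02516 = 180.

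The 127 reproduces as a two-look design at one-sided 0.2 with rho = 2 spending at 73 of 127 events. This gives an interim boundary of HR 1.453, a final alpha of 0.186, and 80.0% power with the futility stop at HR = 1. None of these depends on delay. At the SAP's two-sided 0.20, 127 events give about 69% power, which is the reference level for the log-rank results below.

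**Continuous endpoints.** Let rho be the partial correlation of delay with the outcome, given what is already in the model. It is an assumption throughout. The standard error is multiplied by sqrt(1 - rho²), and the equivalent gain on the main contrast (104 + 52 = 156) is 156 × [1/(1 - rho²) - 1].

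| rho | SE factor | SE reduction | Equivalent patients of 156 |
|---|---|---|---|
| 0 | 1.000 | 0% | 0 |
| 0.2 | 0.980 | 2% | 6.5 |
| 0.3 | 0.954 | 5% | 15.4 |
| 0.4 | 0.917 | 8% | 29.7 |

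**Where baseline is already in the model (6.4.2.1).** A simulation assumed straight-line decline of 0.2 to 0.5 log10 per day, individual slopes and delay uniform over 0 to 5 days. Given baseline, delay explained about 0% to 2.3% of the remaining variance in change at Days 3, 5 and 10. At the top of that range the SE falls by 1 - sqrt(1 - 0.023) = 1.2%, or 156 × (1/0.977 - 1) = 3.7 patients. The result depends on the assumed curve. With a viral peak near onset the share was about 1% to 9%. With a peak about two days after onset it was about 16% to 39%, and it moves with the assumed rate of rise. The documents do not favour any of these curves.

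**Where no covariate is in the model (6.4.2.2).** Under the same straight-line assumptions, delay alone explained about 6% to 22% of AUC variance. The interval would narrow by 1 - sqrt(0.94) = 3% to 1 - sqrt(0.78) = 12%. In that model baseline viral load accounts for more of the AUC than delay does, and delay adds little once baseline is included. Both terms are therefore needed in the fix, and the 3% to 12% should not be credited to delay on top of baseline.

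**Time to resolution (6.4.1).** Simulated log-rank power was computed for 156 patients with exponential resolution times, follow-up to 28 days, conditional HR 1.4, delay uniform over 0 to 5 days and two-sided 0.20:

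| Assumed recovery HR per day of delay | Unstratified | Stratified 0-2 vs 3-5 days |
|---|---|---|
| 1.0 | 68.5% | 68.2% |
| 1.1 | 67.5% | 67.8% |
| 1.2 | 64.6% | 67.3% |
| 1.3 | 59.9% | 65.0% |
| 1.5 | 51.2% | 61.3% |

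The loss if delay is irrelevant is 0.3 points. The gain is about 10 points at the strongest assumed value.

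**Chance imbalance.** With delay uniform on 0 to 5 days, SD = sqrt(35/12) = 1.71. The mean difference between 104 and 52 patients has SE 1.71 × sqrt(1/104 + 1/52) = 0.29 day. Differences up to about 1.96 × 0.29 = 0.57 day are ordinary.

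**The case against.** The strongest reply is that the SAP's analyses are valid as they stand. Randomization balances delay in expectation, the unadjusted tests and intervals already allow for chance imbalance, and entry is limited to a narrow window. Neither document says that delay predicts viral decline or recovery once baseline is known. All of this stands, and it limits the point to efficiency.

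Three stronger readings are tempting, and the documents support none of them:

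- A reader might infer that the estimates are biased. They are not; delay is a pre-treatment variable in a randomized comparison.
- A reader might infer that a known, predictable source of variation is being discarded, chiefly in 6.4.2.1. Its strength is not stated anywhere, and that model already holds baseline viral load and its interaction with visit, which may carry most of what delay would add.
- A reader might scale the gain to all 208 randomized patients and obtain about 9, 21 and 40. The main contrast uses 156, so those counts are one third too high for it.

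It can also be said that SAP 6.3.4 has an imputation rule for incomplete birth dates but none for onset dates, so a partial date could drop a patient from a model. That is correct but minor, because inclusion criterion 4 cannot be checked without knowing when symptoms began.

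**Conclusion.** The omission is confirmed: days from first symptom to first dose is derived and then used in no efficacy model, test or stratum. It is a matter of precision and unadjusted chance imbalance. The clearest gap is the treatment-only AUC model, where baseline viral load is missing as well.

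The size is unknown. Assumed partial correlations of 0 to 0.4 give a standard error reduction of 0% to 8%, or 0 to about 30 patients of 156. For 6.4.2.1 the gain may be near zero. For the primary log-rank test, stratification changes power by between -0.3 and about +10 points across the assumed range. These figures rest on assumed prognostic strengths and, where simulated, on assumed viral and recovery curves and a uniform delay. The case for the change is that it uses data already collected, cannot bias the comparison if pre-specified, and costs little if delay turns out not to matter.

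**What to change.** Make these changes before unblinding, including before anyone able to alter the SAP sees interim efficacy data by arm:

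1. **SAP 6.4.2.2:** replace the ANOVA with an ANCOVA containing treatment, baseline log10 viral load and days from first symptom to first dose (continuous).
2. **SAP 6.4.2.1 and 6.4.3.4:** add the same delay term and its by-visit interaction.
3. **SAP 6.4.4:** add a sensitivity analysis of time to sustained resolution with a log-rank test stratified by delay, for example 0-2 versus 3-5 days.
4. **SAP 6.3.4:** state a simple rule for a partial or missing symptom-onset date so that no patient leaves a model for that reason.

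The cost is SAP wording and programming with a variable already derived, about one degree of freedom per visit in the repeated-measures models, and two in the AUC model. No new data are needed.

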#### 6.4.2.2 AUC in log10 Viral Load

The area under the curve (AUC) of log10 viral load, as assessed using the saliva and as assessed using the nasal swab, will be calculated from randomization to Day 10 and summarized by treatment group using descriptive statistics (N, mean, median, standard deviation, Q1, Q3, minimum, and maximum). The AUC will be calculated using the trapezoidal rule on the period from baseline to Day 10. In subjects who will not have a viral load assessment up to Day 10, the last observation carried forward will be used so that the AUC is calculated on 10 days in all subjects. An ANOVA model will be performed to analyze the difference between treatment groups. The model will include only the treatment group. Contrasts under this model will allow for the comparisons across treatment groups. The results will be presented as mean treatment difference with associated 80% CI and p-value.

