### 3. INVESTIGATION PLAN

#### 3.1. Overall Study Design and Plan Description

This is a randomized, double-blind, multicenter, Phase 2a proof-of-concept study in outpatients with confirmed, mild to moderate, symptomatic COVID-19. Dalcetrapib inactivates the 3CLMpro enzyme of Corona virus and therefore stops the viral replication and transcription in cells. It is being planned to use for treatment in patients with COVID-19.

Up to 60 sites in the United States and Canada, and other countries as appropriate based on the pandemic situation, are planned to enroll patients.

Total duration of study participation is up to 32 days. The screening period is planned to occur between 48 to 24 hours prior to dosing. Randomization will occur during the Screening/Baseline visit in order for treatment to be dispensed in time for start of first dose on Day 1. Patients will either receive dalcetrapib 900, 1800, or 3600 mg or placebo for 10 days and be followed for 18 days of follow-up. The study design is summarized in [Figure 2](#).

It is anticipated that 208 patients will be randomized in one of the dalcetrapib treatment arms or placebo (52 patients to each of 900 mg, 1800 mg, 3600 mg and placebo) for 10 days. Patients will be randomized and receive first dose of study drug within 72 hours of receiving a positive PCR or Point-of-care test for SARS-CoV-2. Patients need to have at least two of the 14 common COVID-19-related symptoms described in the inclusion criteria rated as mild or moderate, as evaluated by ePRO assessment. Symptoms will be assessed at each study visit daily for the first 10 days, then at Day 14 and Day 28, and as clinically indicated. Symptoms will be evaluated as absent, mild, moderate, or severe depending on their impact on activity of daily living.

[figure not shown]
SARS-CoV-2 viral loads will be obtained by both saliva (Oragene) collection and mid-turbinate nasal swab self-collected under supervision of healthcare professional (virtual or home visit) at Screening/Baseline, Day 1, Day 3, Day 5, Day 7, Day 10, and Day 28. Patients who require hospitalization after initiation of study treatment will be followed for vital status through Day 28.

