**APPENDIX 2**

To classify the symptom score and viral load assessments to their appropriate visit identifier, the difference in days between the date of the assessment and the date of the first dose will be calculated, and this difference will be classified according to the reporting windows below. This algorithm will ensure that Day X for symptom score will correspond to Day X for viral load. As per the study protocol, Day 1 corresponds to the date of 1st dose in which all assessments were to be done PRIOR to first dose.

Once the visit identifiers are sorted out, Day 1 will be used to establish a baseline visit. If a subject has no Day 1 assessment but a screening one, then the screening assessment is chosen.

In cases where more than one assessment falls within the same reporting window, the first assessment will be chosen.

Note: For the symptom score, if both ePRO and eCRF assessments were done on the same day, then the ePRO was favored.

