**Reporting windows for the classification of the visit identifiers for symptom score and viral load\***

VISIT**	SCHEDULED WINDOW (± DAYS)	DIFFERENCE BETWEEN DATE OF ASSESSMENT AND DATE OF 1 ST DOSE
*Screening	---	<0
*DAY 1	---	0
DAY 2	---	1
DAY 3	---	2
DAY 4	---	3
DAY 5	---	4
DAY 6	---	5
DAY 7	---	6
DAY 8	---	7
DAY 9	---	8
DAY 10	---	9
Follow-up visit 1 (DAY 14)	±2	11 to 15
Follow-up visit 2 (DAY 28/EOS)	±2	25 to 29

\*Screening and Day 1 will not be reported separately but will be used to classify the baseline visit as detailed above.

\*\*Viral loads are presented ONLY at baseline, Day 3, Day 5, Day 7, Day 10 & Day 28/EOS.

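### The viral-load AUC is compared without adjusting for baseline viral load, and its start is stated in two ways

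*SAP*

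**What the plan says.** SAP section 6.4.2.2, under Key Secondary Analysis, defines an AUC of log10 viral load for saliva and for nasal swab and compares arms by ANOVA: "The model will include only the treatment group". Section 6.4.2.1 models change from baseline in the same variable with treatment, visit and their interaction, "as well as baseline value of log10 viral load and baseline value of log10 viral load-by-visit-interaction".

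On timing, section 6.4.2.2 makes three statements:

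- The AUC "will be calculated from randomization to Day 10".
- In the next sentence: "The AUC will be calculated using the trapezoidal rule on the period from baseline to Day 10".
- The last observation is carried forward where needed, "so that the AUC is calculated on 10 days in all subjects".

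Protocol section 3.1 says: "Randomization will occur during the Screening/Baseline visit". The Schedule of Assessments puts that visit at Day -2 to -1. For viral load, SAP section 6.4.2.1 and Appendix 2 take baseline from Day 1, the date of first dose. Otherwise: "If a subject has no Day 1 assessment but a screening one, then the screening assessment is chosen". The note to the reporting windows adds: "Screening and Day 1 will not be reported separately but will be used to classify the baseline visit as detailed above".

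**The concern.** The AUC is of log10 viral load itself, not of change from baseline. Its first trapezoid point is therefore a value that treatment cannot affect, and the rest of the curve is likely to correlate with it. Leaving baseline out of the model puts that between-patient variation into the error term. The SAP gives no reason for adjusting one viral-load analysis and not the other.

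SAP section 1 says viral-load results are to weigh more in the proof-of-concept decision. The AUC is the one analysis that reduces viral load over the treatment period to a single number. It is also the only one of the two quantitative viral-load models to use Day 7, because the section 6.4.2.1 model takes Days 3, 5, 10 and 28. At stake are the width of its interval and whether the AUC is defined well enough to be computed in only one way.

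**Working it through.** Neither document gives an SD, target difference or power for the AUC. The only sizing figure, 127 resolution events, concerns the symptom endpoint. The stated length of 10 days is the one figure that can be checked.

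**1. Length of the AUC.** Appendix 2 assigns day differences of 0 to Day 1 and 9 to Day 10.

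| First sample | Trapezoid weights (first sample, Days 3, 5, 7, 10) | Elapsed days |
|---|---|---|
| Day 1 | 1, 2, 2, 2.5, 1.5 | 9 |
| One day before first dose | 1.5, 2.5, 2, 2.5, 1.5 | 10 |
| Two days before first dose | 2, 3, 2, 2.5, 1.5 | 11 |

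The SAP does not say whether the trapezoid uses actual dates or visit labels. With actual dates, a Day 1 start gives 9 elapsed days and a screening start gives 10 or 11, so 10 days is not met in all patients. With a Day 1 start, baseline carries 1 of 9 weight-days (11%).

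**2. Precision lost by omitting baseline.** Let r be the correlation between baseline and AUC within arm (an assumption). Adjustment multiplies the residual variance by 1 - r², so the unadjusted interval is wider by the factor 1/√(1 - r²).

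The comparison is 1800 + 3600 mg against placebo, 104 against 52 patients, at the SAP's two-sided 0.20 level. In SD units the standard error is √(1/104 + 1/52) = 0.170. For an illustrative true difference of 0.30 SD, power is Φ(0.30/(0.170·√(1 - r²)) - 1.282).

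| r (assumed) | Unadjusted CI relative to adjusted | Power, adjusted |
|---|---|---|
| 0 | 1.00 | 69% (same as unadjusted) |
| 0.3 | 1.05 | 72% |
| 0.5 | 1.15 | 78% |
| 0.7 | 1.40 | 88% |

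**3. Plausible values of r.** Suppose the five values have equal variance and are mutually independent. Then r = 1/√(1² + 2² + 2² + 2.5² + 1.5²) = 1/√17.5 = 0.24, and the unadjusted interval is about 3% wider. With an equal pairwise correlation of 0.2 to 0.5, r is 0.47 to 0.71. With autoregressive correlation of 0.5 to 0.7 per two days, r is 0.47 to 0.64. Simulating four arms of 52 at the ends of these ranges gave ANCOVA-to-ANOVA standard error ratios of 0.70 to 0.88. Type I error was 0.18 to 0.20 for both models.

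**4. Cost of adjusting if r = 0.** With 208 - 4 = 204 residual degrees of freedom and k added covariate terms, the width factor is √(1 + k/(204 - k - 1)), times a t-quantile ratio very close to 1.

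- Baseline only (k = 1): 1.0025. Adjustment gains once r exceeds about 0.07.
- Baseline plus two strata factors (k = 3): 1.0075. It gains once r exceeds about 0.12.

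**5. Chance imbalance.** Alpha holds on average, but not conditionally on an observed baseline difference. Given a baseline difference of 1.28 standard errors, the unadjusted test's type I error is 0.21, 0.24 or 0.30 for r = 0.3, 0.5 or 0.7.

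**6. Effect of unequal spans, only if actual dates are used.** Simulated profiles covered 15 settings of 200,000 each: mean baseline 5 to 6 log10, baseline SD 0.8 to 1.8, and three rules for values below detection. Screening baselines were split equally between Day -1 and Day -2. If 5% of patients fall back to screening, the AUC SD rises by 1 to 4%. If 20% do, it rises by 4 to 13%. Dividing each AUC by its span keeps the SD within about 1% of the fixed-interval value.

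**The case against.** An unadjusted ANOVA is valid under randomization, so the point is one of efficiency. The AUC is not among the endpoints in SAP section 4.2, and the listed change-from-baseline endpoint is adjusted. Treatment-only models are also the SAP's convention for hospitalization, oxygen therapy and mortality. All of this stands and limits the weight of the point.

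The size of the gain is not established, because r, the AUC's SD and the 0.30 SD difference are not in the documents. That also stands. But the pessimistic case of independent values still gives r = 0.24, above the break-even values of 0.07 and 0.12, so the direction is secure.

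On timing, 10 days can be read as an inclusive count from Day 1 to Day 10, and a constant relabelling changes no p-value. The sentence with the trapezoid rule names baseline, and Days 3 to 10 are single-day windows. Programmers who both follow that sentence could therefore differ only for patients who fall back to screening, and that share is unknown. This narrows the practical effect but does not reconcile the two stated starts or say where in time a screening value is placed. The range of 10 or 11 days is itself incomplete, since a footnote to the Schedule of Assessments allows screening up to 72 hours before first dose.

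Finally, the section 6.4.2.1 model has no strata terms, and the SAP supersedes the protocol's general rule on stratified models. Leaving strata out is thus a specified choice, and no gain from them has been calculated. Baseline is the core of the change.

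**Conclusion.** The concern holds. The AUC analysis omits a collected covariate that is part of its own outcome and that the companion model uses. The test is unbiased; what is lost is precision. The unadjusted interval is about 3% wider if later values are independent of baseline and of one another, and 5% to 40% wider for r from 0.3 to 0.7. All of these figures rest on an assumed r. Separately, and without any such assumption, the two stated starts are different time points, and 10 days in every patient cannot hold in elapsed time. Section 6.4.2.2 should be changed, but the trial's listed viral-load endpoint is not affected.

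**What to change.** In SAP section 6.4.2.2:

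- Replace the ANOVA by an ANCOVA with treatment, baseline log10 viral load from the same specimen type, and the two randomization strata (symptom severity, age). Keep the planned contrasts and 80% intervals.
- State one start. Either place the baseline value at Day 1, including when it comes from screening, and compute the AUC over the fixed 9 days to Day 10; or use actual dates and divide each AUC by its span to give a time-weighted average.
- Reword "will be calculated from randomization to Day 10" and "so that the AUC is calculated on 10 days in all subjects" to match.

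The cost is SAP wording and a few lines of code, with all data already collected. The model uses three of 204 residual degrees of freedom. Patients without a baseline sample drop out of the model, but an AUC that starts at baseline is not defined for them anyway.
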